2. STUDY OBJECTIVES AND ENDPOINTS

The objectives of this study are to:

- Describe the risk of serious and pre-specified opportunistic infections (including tuberculosis) associated with current or recent treatment with etanercept in paediatric plaque psoriasis;

- Describe the long-term risk of incident malignancy in paediatric plaque psoriasis patients who have ever received etanercept;
- Identify any new, serious potentially unrecognised adverse drug reactions (ADRs) by collecting serious adverse event data in this population; and
- Assess effectiveness by describing patterns of treatment with etanercept, including premature discontinuation of etanercept and subsequent treatment with systemic therapies (including re-treatment with etanercept).

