2.1.2. Effectiveness Endpoints

The primary focus of this registry is safety; it will not directly measure effectiveness endpoints. However, to the extent possible effectiveness (or lack of effectiveness) will be

inferred from patterns of treatment and re-treatment. The recommended course of etanercept treatment for paediatric psoriasis is for 24 weeks; physicians are advised to consider discontinuation of etanercept if a satisfactory response is not achieved by 12 weeks. If a patient receives etanercept for less than 24 weeks, the RP will be asked to report the reason for early discontinuation of therapy whether for positive (e.g., clearing of plaque psoriasis) or negative reasons (e.g., intolerance, adverse event, less than expected therapeutic effect). Treatment discontinuation for lack of desired therapeutic effect will, for purposes of analysis, serve as a proxy for treatment effectiveness.

As etanercept is not a cure for this chronic condition, patients will likely require repeated courses of etanercept over time. For each subsequent course of etanercept, occurrence and reasons for premature discontinuation, i.e., less than 24 weeks, will be documented. If a subsequent course of systemic therapy does not include etanercept, the reason for that decision will also be documented.

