7.4. Primary Analyses

It is anticipated that the etanercept treatment status for each patient will change throughout follow-up. A standard course of etanercept treatment is expected to last 24 weeks. Patients successfully responding to the first etanercept treatment course may be exposed to subsequent treatment (i.e., when patients experience a flare) and the time window between two (or more) consecutive courses of treatment may vary substantially.

Patterns of treatment with etanercept will be described (to the extent possible) as follows:

- Frequency of premature discontinuation of etanercept (i.e., treatment course < 24 weeks)
- Frequency of subsequent treatment with systemic therapies (including re-treatment with etanercept)
- Intervals between etanercept treatment and subsequent course of systemic therapy (including etanercept)
- Means and percentages of demographic and disease characteristics of patients who experience and those who do not experience discontinuation of etanercept
- Frequency of discontinuation stratified by cumulative dose, duration of use, and other etanercept use patterns.

Serious and Pre-specified Opportunistic Infections

Time at risk of serious and pre-specified opportunistic infections will correspond to current/recent treatment with etanercept. Current/recent etanercept treatment will be defined as time between the dates of first and last dose within a treatment course plus 28 days. Risk will be estimated as number of events over cumulative time at risk. Estimates of relative risk of these infections will be used to quantify any association between the study outcomes and current/recent treatment with etanercept. In order to calculate relative risk, incidence of infection during cumulative current/recent treatment with etanercept will be compared to incidence of infection during cumulative period without use of etanercept.

Should any patient develop tuberculosis (TB) during the course of follow-up, the Sponsor will conduct standardised incidence ratio (SIR) analyses using geographically appropriate population based rates of TB applied to time at risk on etanercept.

Analyses may include more than one episode of infection experienced by a single individual. Stratified analyses of the events of interest by etanercept dose, duration of treatment, and

number of treatment course (i.e., first, second, etc.) will be attempted, depending on the number of events reported.

Malignancies

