##### **CURRENT/RECENT TREATMENT VERSUS PAST TREATMENT**

In order to interpret reported events, time at risk of occurrence is established based on current or recent (within 28 days) exposure and past exposure.

**Past exposure** is defined as any exposure to etanercept, at any dose, with no reported exposure within the last 28 days.

**Current/recent exposure** is defined as on active etanercept treatment at the time of the event, or last dose of treatment within 28 days (inclusive) preceding the event.

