## PURPOSE SAP

### Protocol # B1801035

- The follow-up time for patients who had malignancies will be censored at the diagnosis date for each type of malignancy. The follow-up time after diagnosis of a malignancy will not be included in the calculation of time at risk or not at risk for the same type of malignancy. However, patients who reported a malignancy are still at risk of having a different type of malignancy. Malignancy types include but are not limited to: Solid malignant tumors, Non-melanoma skin cancers, Malignant tumors of hemopoietic and lymphoid tissues, Carcinoma in-situ.
- Time at risk (in years; for the current/recent etanercept-treated group only) of serious or pre-specified opportunistic infection (excluding malignancies) and other SAEs (excluding serious or pre-specified opportunistic infection and malignancies), respectively: cumulative period of etanercept exposure defined as the sum of each etanercept treatment period,  $[\text{date of last dose} - \text{date of first dose} + 1 + 28]/365.25$ .
- Time not at risk (this applies to time in years accrued after discontinuation of etanercept while followed in the registry, and excludes malignancies) of serious or pre-specified opportunistic infection and other SAEs, respectively: cumulative period without current/recent use of etanercept  $\{[(\text{date of study discontinuation}) - (\text{date of last dose} + 28) + 1] + [\text{intervals between treatment periods} > 28 \text{ days}]\}/365.25$ . For analysis purposes, time not at risk is the total study follow-up time minus the time at risk, which is defined above.
- Incidence rate is calculated as the number of individual events observed during the time at risk, divided by the total number of patient-years at risk for the event, multiplied by 100. Please note that the time at risk for malignancy will be censored at the diagnosis date of that specific malignancy.

In the example below, all person-time in blue would contribute to the ‘current/recent’ category, while all person-time in yellow would contribute to the ‘past treatment’ category for the assessment of SAEs and serious or opportunistic infections. Patients would be considered at risk of malignancies in both the blue and yellow periods.

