### **7.3 Risk of infection associated with etanercept exposure**

The following patient listings will be generated:

- All serious and opportunistic infections
  - Serious (infection site, pathogen, onset date, resolution date or ongoing, date of last etanercept dose prior to infection)
  - Opportunistic (infection type, nosocomial, onset date, resolution date or ongoing, date of last etanercept dose prior to infection)
  - Concomitant therapies (all) within 28 days prior to each infection
  - Immunosuppressant/steroid use within 28 days prior to each infection

In addition, the following tabular summaries will be presented:

- Number of unique patients, total number of events, and incidence rate of all reported serious and opportunistic infections (by MedDRA System Organ Class (SOC) and Preferred Term (PT))
- Overall incidence rate, stratified by exposure type (current/recent and past)
- Overall incidence rate, stratified by treatment period ( $\leq 24$  weeks,  $> 24$  weeks) during any period of etanercept treatment
- Summary of use of other immunosuppressants or steroids within 28 days prior to serious and opportunistic infection
- Summary of baseline characteristics (demographic and clinical characteristics) stratified by infection status (none reported, reported in association with current or recent exposure, reported in association with past exposure, and specifically associated with initial course)
- Summary of number of infections reported per patient (overall and by exposure status)
- If an adequate number ( $\geq 5$ ) of infections are recorded in each of the current/recent and past treatment groups, relative risk (95% CI) of infection will be calculated as the

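### The infection rate ratio compares etanercept time with off-etanercept time that may include other systemic immunosuppressants or biologics, and no planned output separates the two

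*Protocol*

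**What the plan says.** **How the comparator is defined.** Protocol 7.4 counts time from first to last dose of a course plus 28 days as current/recent etanercept. The infection rate in that time is then "compared to incidence of infection during cumulative period without use of etanercept". SAP 5.3.1 defines past exposure as "any exposure to etanercept, at any dose, with no reported exposure within the last 28 days". SAP 6.6 describes the comparator time as "cumulative period without current/recent use of etanercept", and adds that "time not at risk is the total study follow-up time minus the time at risk, which is defined above". All three definitions depend on etanercept dosing alone.

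**How it is used.** SAP 7.3 reports the overall infection rate by exposure type (current/recent and past) with no minimum number of events. If each category has at least 5 infections, it also reports a crude incidence rate ratio with an exact 95% interval. There is no stratification, adjustment, or exclusion of time on other drugs.

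**What is expected after etanercept.** The effectiveness objective in Protocol 2 covers "subsequent treatment with systemic therapies", a term that there includes a return to etanercept as well as other drugs. Protocol 2.1.2 plainly foresees other drugs: "If a subsequent course of systemic therapy does not include etanercept, the reason for that decision will also be documented". Protocol 4.3 bars only biologics used before entry. Neither document ends follow-up at a later switch.

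**How other therapy enters the infection analysis.** SAP 7.3 plans a "Summary of use of other immunosuppressants or steroids within 28 days prior to serious and opportunistic infection", with listings over the same look-back.

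**The concern.** Etanercept is licensed here for severe disease in children whom other systemic treatment or phototherapy has not controlled, or who cannot tolerate it. Some of them will move to another systemic drug after etanercept, and Protocol 1 names cyclosporin, methotrexate and several biologics as options. That time falls into the past category alongside time on no systemic drug, so the reference rate is a mixture. Time on etanercept can likewise include concomitant immunosuppressants.

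The planned look-back cannot undo this. It counts drug use among infections but not the person-time on the same drugs, so no rate with and without other therapy can be formed.

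Infection risk is the first objective of a safety study that is a condition of marketing authorisation. Protocol 7.6 offers the within-registry contrast because there is no untreated group, and its limitations do not mention replacement therapy. SAP 5.4 calls the inclusion of suitable covariates critical, yet this comparison uses none. A ratio near 1 could be read as no added risk when it may only show a risk similar to that of the next drug. A raised ratio could partly reflect co-medication.

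**Working it through.** The plan states no infection rate, expected event count or ratio for this comparison, so there is no figure to reproduce. The check has three parts.

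**1. Size and direction of the bias**

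The following are assumptions; the documents give none of them:
- θ: true rate ratio, etanercept versus no systemic therapy
- p: share of off-etanercept time on replacement therapy, and RRs its infection rate ratio
- q: share of etanercept time with concomitant immunosuppressants, and RRc their rate ratio

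Crude ratio = θ × [(1 − q) + q·RRc] / [(1 − p) + p·RRs]

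The bias is downward if p(RRs − 1) > q(RRc − 1), upward if the inequality is reversed, and nil if the two sides are equal.

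With θ = 2 and q = 0:

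| p | RRs = 1.5 | RRs = 2 | RRs = 3 |
|---|---|---|---|
| 0.25 | 1.78 | 1.60 | 1.33 |
| 0.50 | 1.60 | 1.33 | 1.00 |
| 0.75 | 1.45 | 1.14 | 0.80 |

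For example, 2 / (0.5 + 0.5 × 2) = 1.33. If RRs = 1 there is no bias. With θ = 1.5, p = 0.5 and RRs = 2, the crude ratio is 1.5 / 1.5 = 1.00.

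With concomitant use during etanercept (θ = 2, RRc = RRs = 2, q = 0.25):
- p = 0.50: 2 × 1.25 / 1.50 = 1.67
- p = 0.25: 2 × 1.25 / 1.25 = 2.00, no net bias
- p = 0.10: 2 × 1.25 / 1.10 = 2.27, bias upward

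**2. What a split would show**

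Assume 150 patient-years on etanercept and 150 off, half of the latter on replacement therapy. Assume a base rate of 3 per 100 patient-years, θ = 2, RRs = 2 and q = 0. Expected infections:
- on etanercept: 150 × 0.03 × 2 = 9.0
- off, no other systemic: 75 × 0.03 = 2.25
- off, on replacement: 75 × 0.03 × 2 = 4.5

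Planned ratio: (9.0/150) / (6.75/150) = 1.33. Ratio against therapy-free time: (9.0/150) / (2.25/75) = 2.00. The planned comparator expects 6.75 events, above the SAP's minimum of 5. The therapy-free comparator expects 2.25, below it.

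**3. Precision**

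With 60 to 80 patients (Protocol 3, SAP 4) followed for 5 years without loss, follow-up is at most 60 × 5 = 300 to 80 × 5 = 400 patient-years. The SAP's exact interval with equal person-time gives:
- 5 versus 5 infections: ratio 1.00, 95% CI 0.23 to 4.35
- 10 versus 5 infections: ratio 2.00, 95% CI 0.62 to 7.46

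**The case against.** **The direction is not fixed.** A reader might infer that mixing in replacement therapy must pull the ratio towards or below 1. The documents do not support that. It presumes a true ratio above 1 and ignores concomitant immunosuppressants during etanercept, although Protocol 1.1 says patients on TNF inhibitors often receive other medications that carry risk of their own (said there of malignancy). The working shows that the bias can cancel or reverse. This objection stands, and it is a reason to split both exposure categories.

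**Much off-etanercept time may be drug-free.** Protocol 2.1.2 and 7.4 expect repeated etanercept courses restarted at flare, so many gaps may involve no other systemic drug. Some systemic options, such as acitretin, are not obviously immunosuppressants. A reader might infer that past time is largely replacement therapy, but nothing in the documents gives that share. This stands against any claim about size, but not against the structural point.

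**Other therapy is described elsewhere.** SAP 7.2 tabulates patients needing further systemic treatment by type, and Protocol 7.4 describes intervals to the next systemic course. It would therefore be wrong to say that such use is examined only in infected patients. But these summaries supply no person-time or infection rates by other therapy.

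**The ratio is descriptive and guarded.** SAP 7.3 labels it as current/recent versus past etanercept, SAP 6.2 calls the study non-comparative, and no hypothesis test is planned. This lowers the stakes. Even so, the exposure-specific rates are reported whatever the event count, and a confidence interval does not reflect the mixing.

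**The therapy-free ratio will often be unavailable, and it has its own bias.** It may miss the five-event minimum, and time free of systemic therapy may be time in remission. Both points stand, so it should be supportive only.

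**Conclusion.** The concern holds as a structural one. The comparator is defined by etanercept dosing alone, the ratio is crude, and no planned output separates off-etanercept time with other systemic immunosuppressants or biologics from time without them. The crude rates and ratio can therefore be confounded by other therapy.

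The direction is conditional: downward if replacement therapy raises infection risk and weighs more off than on etanercept, upward if concomitant use weighs more on etanercept. In the assumed cases, a true ratio of 2.0 appears as anything from 0.80 to 2.27. The actual size cannot be derived from the documents.

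Practical impact is limited by few events and wide intervals: at the SAP's minimum of 5 versus 5, the interval covers every shift shown above. This is a cheap improvement to a descriptive analysis and does not invalidate the plan.

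**What to change.** In SAP 6.6 and 7.3:

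1. Define in advance which drugs count as another systemic immunosuppressant or biologic, and apply the same 28-day carry-over as for etanercept.
2. In both the current/recent and past categories, tabulate person-time, infections and rates with exact 95% intervals, split by such use (yes/no).
3. Keep the crude ratio. Add the ratio of current/recent etanercept against past time free of such therapy as a supportive analysis, only when the SAP's five-event minimum is met in each group. Otherwise show rates only.
4. State beside the crude ratio that its reference is past etanercept time, which may include other systemic therapy, and beside the supportive ratio that therapy-free time may reflect milder disease.

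**Cost.** Some programming, and sparse cells. No new data item should be needed: Protocol 2.2 and SAP 5.3.2 collect dose and duration of other treatments, and SAP 5.4 has medication exposures updated at each follow-up. The documents state start and stop dates only for etanercept periods, and the case report form was not available. That other medications can be dated well enough is therefore an assumption. It is a reasonable one, because the planned intervals to the next systemic course and the 28-day look-backs already need that timing. Where timing is incomplete, report the amount of unclassified person-time.

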4.2. Inclusion Criteria

To be eligible for registry enrolment, patients must meet all of the following criteria:

- Age ≤ 17 years at time of administration of the first dose of etanercept
- Diagnosis of plaque psoriasis by a dermatologist
- Prior to enrolment, a clinical decision has been made to prescribe etanercept for the treatment of psoriasis
- Newly prescribed with initial etanercept or actively being treated with etanercept, regardless of length of treatment prior to study enrolment
- Capable and willing to provide paediatric assent, or written informed consent when applicable, and
- Parent(s)/legal representative of patient is capable and willing to provide written informed consent

- Evidence of a personally signed and dated informed consent document indicating that the patient (or a legally acceptable representative) has been informed of all pertinent aspects of the study must exist.

Please note: Currently etanercept is approved for the treatment of severe plaque psoriasis in children and adolescents from the age of 6 years who are inadequately controlled by, or are intolerant to, other systemic therapies or phototherapies. The registry protocol will not encourage use of etanercept at younger ages. However if a doctor, in collaboration with the child's parents, makes the independent clinical decision to prescribe etanercept to a child less than 6 years of age for severe plaque psoriasis, that child may be included in the registry.

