7.1. General considerations

All AE verbatim terms will be recorded and coded using MedDRA. Statistical analysis of all data will be performed using SAS[®] statistical software (SAS Institute, Cary, NC, USA).

Frequencies of defined outcomes will be described. If possible, analyses will also be performed using the different etanercept treatment status (i.e., current/recent versus past treatment) and etanercept cumulative dose exposure groups.

Analysis of the characteristics of patients enrolled in the registry and of those who did not consent to participate (to the extent feasible) will help evaluate whether there are any differences between registry enrollees and non-respondents, i.e., generalizability.

Primary analyses will be limited to prospective data, i.e., events reported during participation in the registry. Serious and pre-specified opportunistic infections and malignancies reported as part of retrospective data collection will be summarized separately.

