Time at risk of incident malignancies will be defined as time since the date of first dose of etanercept treatment to the date of malignancy diagnosis or end of follow-up if no malignancy has been diagnosed. Long-term risk of incident malignancy in patients who have ever received etanercept will be estimated as number of events over the total time at risk. Should any patient develop cancer during follow-up, the Sponsor will calculate SIRs for malignancy (age and gender-adjusted) using geographically appropriate population-based norms. Although all malignancies reported throughout the study will be described, only the first diagnosis of malignancy occurring during the follow-up will be considered in the SIR analysis.

Other SAEs

Time at risk of all other SAEs will correspond to current/recent treatment with etanercept. Current/recent etanercept treatment will be defined as time between the dates of first and last dose within a treatment course plus 28 days.

A descriptive analysis of SAEs will be conducted. Any grouping and stratification will be dependent on the number and type of events reported.

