## **PURPOSE SAP**

**Protocol # B1801035**

Any patient who receives at least one dose of etanercept will be included in the evaluation for safety. The primary focus of this Registry is safety; however, to the extent possible effectiveness (or lack of effectiveness) will be inferred from patterns of treatment and re-treatment. In addition, the change of severity of plaque psoriasis as a measure of effectiveness will also be assessed, if these data are available among the majority of patients.

Primary analyses will be limited to prospective data, i.e., events reported during participation in the registry. Serious and pre-specified opportunistic infections and malignancies reported as part of retrospective data collection will be included in a summary of medical history and co-morbid conditions.

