#### **6.6 Derivations**

The following derived/calculated values will be used:

[figure not shown]
- Age at enrollment in years:  $[\text{date of enrollment} - \text{date of birth} + 1] / 365.25$
- Duration of disease at enrollment in years:  $[\text{date of enrollment} - \text{date of diagnosis} + 1] / 365.25$
- Cumulative exposure in weeks by the duration of chronic exposure for each period of etanercept exposure:  $[(\text{last dose date} - \text{first dose date} + 1) + 28] / 7$ . A treatment period is defined as continuous treatment with no interruptions of more than 28 days. Restarting treatment within 28 days is considered as having continuous exposure
- Duration of each etanercept treatment period (in weeks):  $(\text{last dose date} - \text{first dose date} + 1) / 7$
- Time at risk of malignancy (in years):  $[\text{date of malignancy diagnosis or end of follow-up if no malignancy is found} - \text{initial treatment dose date} + 1] / 365.25$

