#### 7.4 Risk of malignancy associated with any etanercept exposure

All malignancies reported will be presented as a listing, including malignancy type (verbatim and MedDRA PT, date of diagnosis and date of resolution (if applicable)), all reported prior drug exposures (up to the time of diagnosis), interval between first etanercept exposure and diagnosis of malignancy, duration of actual exposure (excluding temporary interruptions, if any), and total cumulative exposure.

Risk of incident malignancy in patients who have ever received etanercept will be estimated as number of events over the total time at risk, defined as the time since first dose. If any patients do develop a malignancy during follow-up, incidence rates will be presented and SIR analyses using geographically appropriate population-based norms (age and gender-adjusted) may be used, depending on the data available:

- Incidence rate and SIR (95% CI), for all cancers reported excluding non-melanoma skin cancer and cancer in-situ (primary analysis)

If any patients develop the following specific type of malignancy during follow-up:

- Incidence rate and SIR (95% CI), limited to hematopoietic cancers (secondary analysis)
- Incidence rate of non-melanoma skin cancer (NMSC), and SIR (95% CI) if appropriate population-based rates for NMSC are available (secondary analysis)

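### Malignancy time at risk starts at the first etanercept dose, even before enrolment, but only malignancies during registry participation count, so the rate and SIR are too low

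*Protocol*

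**What the plan says.** **Denominator.** The malignancy paragraph of Protocol 7.4 sets the start of the clock: "Time at risk of incident malignancies will be defined as time since the date of first dose of etanercept treatment". SAP 7.4 divides events by the "total time at risk, defined as the time since first dose". The formula in SAP 6.6 subtracts the initial dose date from the diagnosis date or end of follow-up. The enrolment date appears in none of the three.

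**Numerator.** Protocol 7.1 is narrower: "Primary analyses will be limited to prospective data, i.e., events reported during participation in the registry". SAP 4 repeats this rule, and says that "malignancies reported as part of retrospective data collection will be included in a summary of medical history and co-morbid conditions". For the SIR, Protocol 7.4 adds that "only the first diagnosis of malignancy occurring during the follow-up will be considered in the SIR analysis".

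**Who can enter.** Protocol 4.2 admits patients "actively being treated with etanercept, regardless of length of treatment prior to study enrolment". Protocol 7.6 confirms that the registry will include patients who started etanercept before enrolling. Protocol 6.2 expects their number to be limited but gives no figure, and neither document gives their prior treatment time. Protocol 4.3 excludes patients with a history of malignancy.

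**The concern.** The person-time and the events are taken over different windows. A child who starts etanercept two years before enrolling brings two years of person-time, and two years of expected count for the SIR, in which no malignancy can enter the primary numerator. If the history-of-malignancy exclusion covers that interval, the time is event-free by design. This is left truncation without adjustment for delayed entry.

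The error has one direction. Whenever any patient has exposure before enrolment, the rate, the SIR and both confidence limits are too low, which favours the product. Long-term malignancy risk is the second registry objective, and the registry is a condition of marketing authorisation.

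**Working it through.** The documents state no expected malignancy rate, expected count or SIR, so there is no figure to reproduce. The check is a direct person-time calculation.

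**Inputs**
- Share of patients with prior use, f: not given; assumed.
- Their mean time from first dose to enrolment, T0: not given; assumed. The indication was authorised on 22 December 2008 and first enrolment was expected in Q4 2010 (Protocol 1.1 and 5), so about 1.8 years of on-label prior use was possible even for the first enrolees.
- Mean follow-up after enrolment, F: 4.5 years assumed. The maximum is 5 years, and less for late enrolees (Protocol 5, Table 0-1). F = 3 and F = 5 are shown as a range.
- Patients: 70, the middle of the 60 to 80 target (Protocol 3).

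**Formula.** Let d = f × T0, the mean pre-enrolment years per enrolled patient. With few events and a roughly constant rate, the planned estimate divided by the delayed-entry estimate is F/(F + d). The relative shortfall is d/(F + d).

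| d (years) | For example | Shortfall at F = 4.5 |
|---|---|---|
| 0.025 | 5% × 0.5 y | 0.025/4.525 = 0.6% |
| 0.05 | 10% × 0.5 y | 0.05/4.55 = 1.1% |
| 0.1 | 10% × 1 y | 0.1/4.6 = 2.2% |
| 0.2 | 10% × 2 y | 0.2/4.7 = 4.3% |
| 0.4 | 20% × 2 y | 0.4/4.9 = 8.2% |
| 0.5 | 25% × 2 y | 0.5/5.0 = 10.0% |

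At d = 0.2 the shortfall is 6.3% for F = 3 (0.2/3.2) and 3.8% for F = 5 (0.2/5.2). A 5% shortfall needs d of at least 0.16, 0.24 or 0.26 years for F = 3, 4.5 or 5. A 10% shortfall needs 0.33, 0.50 or 0.56 years.

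**SIR.** If the background rate before enrolment is r times the rate during follow-up, the factor is F/(F + r × d). With d = 0.2 and F = 4.5, the shortfall is 2.2%, 4.3% and 6.2% for r = 0.5, 1 and 1.5.

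**Simulation.** With a true SIR of 1, f = 25%, T0 = 2 years, F = 5 years and patients with a pre-enrolment malignancy kept out, the planned SIR came to 0.90 and the delayed-entry SIR to 0.99. The formula gives 5/5.5 = 0.91.

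**Prospective stratum.** SAP 6.5 classes as prospective anyone who started no more than 30 days before enrolment. Each such patient can add at most 30/365.25 = 0.082 years, so the shortfall in that stratum is at most 1.8% at F = 4.5 (1.6% at F = 5, 2.7% at F = 3).

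**Against Poisson error.** One malignancy, 70 patients, exact 95% limits:

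| Person-years | Rate per 100 (95% CI) |
|---|---|
| 70 × 4.5 = 315 (delayed entry) | 0.317 (0.008 to 1.769) |
| 70 × 4.7 = 329 (planned, d = 0.2) | 0.304 (0.008 to 1.694) |
| 70 × 5.0 = 350 (planned, d = 0.5) | 0.286 (0.007 to 1.592) |

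For one event the upper limit is 5.572/0.0253, or about 220 times the lower.

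**The case against.** **The text may already match the two windows.** SAP 6.6 says: "Incidence rate is calculated as the number of individual events observed during the time at risk". It also places patients at risk of malignancy in both the current/recent and past-treatment periods of its example, and sets time not at risk equal to total study follow-up minus time at risk. Together these could imply a clock that starts at enrolment, and restricting the analysis to prospective data could be read as restricting person-time too. This does not hold. The time-not-at-risk definition expressly leaves malignancies out. Both documents explain prospective data in terms of events only. The three explicit definitions all start at first dose. The colour-coded example is not visible in the text available, so the point rests on the written formulas.

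**The bias is disclosed.** Protocol 7.6 warns of depletion of susceptibles among prior users and of underestimated risk. The direction and the affected group are the same, but that is a selection effect. The protocol does not mention the surplus person-time, which a derivation can remove.

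**Results by enrolment type, or a sensitivity analysis, would do.** Reporting the prospective stratum would nearly remove the bias there, but nothing limits the SAP 7.4 malignancy analysis to that stratum. A delayed-entry sensitivity analysis would expose the problem while leaving the wrong figure as the main result.

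**The effect is small and conditional.** This stands. SAP 7.4 presents incidence rates only if a malignancy occurs, and the SIR is conditional too. No zero-event upper limit is specified; any that was reported would fall by the same factor. The study is descriptive, plans no hypothesis test, and says itself that SIRs may be of limited value. The 8% to 10% figures need a share of prior users that the documents do not suggest.

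**Conclusion.** The plan is wrong as written: its definitions put pre-enrolment years into the malignancy denominator and the SIR expected count while keeping any event in those years out of the numerator. The downward direction is certain if any patient started before enrolment, and the bias is zero if none did.

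The size cannot be determined from the documents. A limited number of prior users points to roughly 0.6% to 4.3%, and 8% to 10% would need d of 0.4 to 0.5 years. All of these figures rest on assumed f, T0 and F and a roughly constant rate. The shift is minor beside the sampling error of a single event and unlikely to change a conclusion. It should still be fixed, because it runs one way in a regulatory safety estimate and costs almost nothing to remove.

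**What to change.** 1. In SAP 6.6 and 7.4, compute malignancy time at risk as [date of malignancy diagnosis or end of follow-up − max(enrolment date, initial dose date) + 1]/365.25.
2. Compute SIR expected counts over the same time.
3. Align the incidence-rate wording in SAP 6.6 with the prospective-events rule in Protocol 7.1 and SAP 4.
4. Keep time since first dose as a descriptive latency variable in the malignancy listing.
5. Record the departure from Protocol 7.4 in the final report.

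Separately, state whether the history-of-malignancy exclusion covers a malignancy diagnosed between first dose and enrolment, and reconcile it with Table 0-1, Protocol 7.1 and SAP 4, which provide for malignancies recorded at enrolment or retrospectively. This does not affect the sizes above.

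**Cost.** One derivation, matching text and a report note. Both dates are already held. The price is slightly fewer person-years (315 instead of 329 in the d = 0.2 example) and a slightly wider interval. Follow-up was due to end in 2018, SAP 5.0 is dated February 2019, and a protocol amendment would usually need authority and ethics submission (Protocol 10.1.2), so the SAP is the practical place for the change.
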